After a Screening visit up to 28 days before Baseline, approximately 200 patients will be assigned randomly in a 1:1:1:1 ratio to receive 1 of the 3 orismilast doses (20 mg, 30 mg, or 40 mg) or placebo twice daily (BID) for 16 weeks, with a 4-week Follow-up visit. Administration will begin at Baseline with a dose titration period. The maximum duration of study participation is approximately 24 weeks.

Patients will be seen at the site on Screening, Baseline (Day 1), and Weeks 1, 2, 4, 8, 12, 16 (End-of-Treatment visit), and 20 (Follow-up visit, 4 weeks after treatment completion or discontinuation). Visits at Weeks 1 and 2 could be conducted via a telemedicine procedure at Investigator's discretion.

At Baseline and each visit from Week 4 onwards, PASI, BSA, IGA, and PSS will be assessed. Quality of life will be assessed by administration of DLQI at Baseline and at Weeks 16 and 20 visits. Additional efficacy parameters include: an ss-IGA, a Physician Global Assessment of fingernail psoriasis (PGA-F), and

These parameters will be assessed at Baseline and Weeks 16 and 20. Safety evaluations include adverse events (AEs), laboratory and vital sign assessments, physical examinations, as well as mood change evaluation by patient (Hospital Anxiety and Depression Scale) and suicidal ideation evaluation by Investigator (C-SSRS). A panel of cardiovascular risk factors will be assessed at Baseline and Week 16.

Before administration of the study drug at Baseline and on Weeks 4, 8, and 16, blood will be collected for orismilast concentration determination.

Selection of Patients:

Main Inclusion Criteria:

- 1. Capable of giving signed informed consent, which includes compliance with the requirements and restrictions listed in the Informed Consent Form (ICF) and in the protocol.
- Male and female patients ≥18 years of age at the time of signing the ICF.
- 3. Body weight of >40 kg at the time of signing the ICF.
- 4. Diagnosis of chronic, stable plaque-type psoriasis at least 2 months before the Screening visit. If the patient is diagnosed with psoriasis arthritis, the arthritis should be stable.
- 5. Moderate-to-severe plaque-type psoriasis as defined by PASI \geq 12, BSA \geq 10%, and IGA \geq 3 at the screening and baseline visits.
- 6. Candidate for systemic antipsoriatic treatment or phototherapy.

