6.2.2.2. Other Secondary Endpoints

• Patients achieving a score of Clear (0) or Almost Clear (1) and an at least 2-point improvement in IGA at Weeks 4, 8, 12, and 20.

- Patients achieving PASI75 response at Weeks 4, 8, 12, and 20.
- Patients achieving 50% reduction in PASI (PASI50) and 90% reduction in PASI (PASI90) response at Weeks 4, 8, 12, 16, and 20.
- Change from Baseline in PASI at Weeks 4, 8, 12, and 20.
- Change from Baseline in total Psoriasis Symptoms Scale (PSS) score at Weeks 4, 8, 12, 16, and 20.
- Change from Baseline in each individual item of the PSS at Weeks 4, 8, 12, 16, and 20.
- Change from Baseline in the affected body surface area (BSA) at Weeks 4, 8, 12, 16, and 20.
- Change from Baseline in Dermatology Life Quality Index (DLQI) score at Weeks 16 and 20.
- Patients experiencing psoriasis rebound by Week 20, defined as PASI ≥125% of Baseline or new generalized pustular, erythrodermic, or more inflammatory psoriasis.

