7. INVESTIGATIONAL PLAN

7.1. Description of Overall Study Design and Plan

This multicenter, randomized, double-blind, placebo-controlled, parallel-group, Phase 2b doseranging study is designed to assess the efficacy and safety of modified-release orismilast compared with placebo in adult patients with moderate-to-severe plaque-type psoriasis. Efficacy and safety outcomes will be evaluated to select an appropriate orismilast dose for subsequent Phase 3 studies. The study will be conducted in approximately 40 centers in Europe and North America.

After a Screening visit up to 28 days before Baseline, approximately 200 patients will be assigned randomly in a 1:1:1:1 ratio to receive 1 of the 3 orismilast doses (20 mg, 30 mg, or 40 mg) or placebo twice daily (BID) for 16 weeks, with a 4-week Follow-up visit. Administration will begin at Baseline with a dose titration period. The maximum duration of study participation is approximately 24 weeks.

Patients will be seen at the site on Screening, Baseline (Day 1), and Weeks 1, 2, 4, 8, 12, 16 (End-of-Treatment [EOT] visit), and 20 (Follow-up visit, 4 weeks after treatment completion or discontinuation). Visits at Weeks 1 and 2 could be conducted via a telemedicine procedure at Investigator's discretion.

N=50 Orismilast 20 mg BID (2 x 10 mg tablets) N=50 Orismilast 30 mg BID Screening (1 x 30 mg tablet and 1 x placebo tablet*) N=50 Orismilast 40 mg BID (1 x 10 mg tablet and 1 x 30 mg tablet) N=50 Placebo BID (2 x placebo tablets)* **Treatment Period** Follow up Randomization End of Period (16 weeks) Treatment (1:1:1:1)

Figure 1. Study Design

Abbreviation: BID, twice a day

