#### Baseline Value

Baseline value will be defined as the last non-missing value recorded prior to the first intake of study treatment.

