**This document is confidential.**

- Patients achieving 50% reduction in PASI (PASI50) and 90% reduction in PASI (PASI90) response at Weeks 4, 8, 12, 16, and 20.
- Change from Baseline in PASI at Weeks 4, 8, 12, and 20.
- Change from Baseline in total Psoriasis Symptoms Scale (PSS) score at Weeks 4, 8, 12, 16, and 20.
- Change from Baseline in each individual item of the PSS at Weeks 4, 8, 12, 16, and 20.
- Change from Baseline in the affected body surface area (BSA) at Weeks 4, 8, 12, 16, and 20.
- Change from Baseline in Dermatology Life Quality Index (DLQI) score at Weeks 16 and 20.
- Patients experiencing psoriasis rebound by Week 20, defined as PASI  $\geq$ 125% of Baseline or new generalized pustular, erythrodermic, or more inflammatory psoriasis.

PASI50 represents the percentage of patients who have achieved a 50% or more reduction in their PASI score from baseline. PASI90 represents the percentage of patients who have achieved a 90% or more reduction in their PASI score from baseline.

Continuous secondary efficacy endpoints will be analyzed using MMRM, similar to the supportive MMRM for the primary endpoint. The same analyses will be repeated on the PP population.

The analysis on categorical secondary efficacy endpoints will be performed using differences in proportions, comparing each active treatment group to placebo in the ITT population with handling of missing data as specified in Section 9. Response by treatment group and difference in response rate and p-values compared to placebo will be presented.

Actual values and change from baseline values of PSS will be summarized by visit using descriptive statistics and presented graphically over time. Actual values, change from baseline values and percentage change from baseline of BSA and DLQI will be summarized by visit using descriptive statistics and presented graphically over time. The percentage of patients with PASI50 and PASI90 will be presented graphically over time. These tables and figures are based on observed cases, thus purely descriptive.

PSS (including change from baseline values) will be listed. BSA and DLQI (including change from baseline and percentage change from baseline values) will be listed.

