	14.2.2.8.4	Actual Values, Change from Baseline in Each Individual Item of the PSS at Weeks 4, 8, 12, 16, and 20 Other Secondary Efficacy Analysis: Descriptive Statistics – Observed Cases	PP Population
	14.2.2.9.1	Change from Baseline in the Affected Body Surface Area (BSA) at Weeks 4, 8, 12, 16, and 20 Other Secondary Efficacy Analysis Mixed Model for Repeated Measures	ITT Population
	14.2.2.9.2	Change from Baseline in the Affected Body Surface Area (BSA) at Weeks 4, 8, 12, 16, and 20 Other Secondary Efficacy Analysis: Mixed Model for Repeated Measures	PP Population
	14.2.2.9.3	Actual Values, Change from Baseline and Percentage Change from Baseline in Body Surface Area (BSA) Other Secondary Efficacy Analysis: Descriptive Statistics– Observed Cases	ITT Population
	14.2.2.9.4	Actual Values, Change from Baseline and Percentage Change from Baseline in Body Surface Area (BSA) Other Secondary Efficacy Analysis: Descriptive Statistics– Observed Cases	PP Population
	14.2.2.10.1	Change from Baseline in Dermatology Life Quality Index (DLQI) Score at Weeks 16 and 20 Other Secondary Efficacy Analysis: Mixed Model for Repeated Measures	ITT Population

This document is confidential.

Header	Table Number	Name	Analysis Population
	14.2.2.10.2	Change from Baseline in Dermatology Life Quality Index (DLQI) Score at Weeks 16 and 20 Other Secondary Efficacy Analysis: Mixed Model for Repeated Measures	PP Population
	14.2.2.10.3	Actual Values, Change from Baseline and Percentage Change from Baseline in Dermatology Life Quality Index (DLQI) Score Other Secondary Efficacy Analysis: Descriptive Statistics– Observed Cases	ITT Population
	14.2.2.10.4	Actual Values, Change from Baseline and Percentage Change from Baseline in Dermatology Life Quality Index (DLQI) Score Other Secondary Efficacy Analysis: Descriptive Statistics– Observed Cases	PP Population
	14.2.2.11.1	Patients Experiencing Psoriasis Rebound by Week 20 Other Secondary Efficacy Analysis – Multiple Imputation	ITT Population
	14.2.2.11.2	Patients Experiencing Psoriasis Rebound by Week 20 Other Secondary Efficacy Analysis – Multiple Imputation	PP Population
	14.2.2.12.1	Percentage of Patients with PASI50, PASI75, PASI90 and PASI100 Response over Time Other Secondary Efficacy Analysis: Descriptive Statistics - Observed cases	ITT Population
	14.2.2.12.2	Patients Achieving 90% reduction in PASI (PASI90) Response at Weeks 4, 8, 12, 16 and 20 Other Secondary Efficacy Analysis - Non-response Imputation	ITT Population

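### The rebound-by-Week-20 endpoint pools on-treatment worsening with worsening after stopping, so it cannot isolate withdrawal rebound, and its comparison with placebo is tilted towards an effective drug

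*Protocol*

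**What the plan says.** Protocol 6.2.2.2 defines the endpoint as "Patients experiencing psoriasis rebound by Week 20, defined as PASI ≥125% of Baseline or new generalized pustular, erythrodermic, or more inflammatory psoriasis". The Protocol synopsis, SAP 5.2 and SAP 9.2.2 give the same definition. It has an end (Week 20) but no starting visit, no link to the last dose, and no condition on earlier response. The other timed endpoints in that list are set at named visits; only rebound is cumulative.

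The reference value is pre-treatment. SAP 7.2 states: "Baseline value will be defined as the last non-missing value recorded prior to the first intake of study treatment".

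On measurement, the Protocol synopsis says: "At Baseline and each visit from Week 4 onwards, PASI, BSA, IGA, and PSS will be assessed". Weeks 4, 8, 12 and 16 fall in the treatment period. The Follow-up visit comes four weeks after completion or discontinuation (Protocol 7.1).

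On analysis, SAP 9.2.2 says the categorical secondary endpoints "will be performed using differences in proportions, comparing each active treatment group to placebo in the ITT population", with p-values. SAP 18 lists Table 14.2.2.11.1 as "Patients Experiencing Psoriasis Rebound by Week 20 Other Secondary Efficacy Analysis – Multiple Imputation" for the ITT population, and Table 14.2.2.11.2 repeats it for the PP population. No table is restricted to post-treatment rebound.

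Two further rules affect visit labels. Protocol 8.4 lets the EOT assessments take place up to four weeks after the last dose. SAP 7.4 can assign a discontinuer's EOT data to Week 4, 8, 12 or 16, and labels the later visit Follow-up rather than Week 20.

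**The concern.** Withdrawal rebound is worsening after study drug is stopped. A patient whose PASI reaches 125% of Baseline at Week 4 while taking tablets meets this definition, and so does a placebo patient whose disease flares at Week 8. Effective treatment prevents such on-treatment worsening, so efficacy alone pulls the active arms' count down. Any genuine post-stop excess in the active arms is then added to a comparison that already favours the drug.

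At stake is what a table headed rebound will be taken to mean. The secondary objective is to identify the dose with the best benefit/risk ratio (Protocol 6.1.2), and this is the only listed endpoint aimed at rebound. A low active-minus-placebo difference could be read as reassurance about stopping the drug when part of it reflects efficacy during treatment.

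**Working it through.** **Inputs (Protocol 15.1, SAP 4.3).** Mean percentage change in PASI: −32.2 on placebo and −50.9 on each dose. SD 33; 50 patients per arm; two-sided 5% test. The documents give no expected rate, margin or power for rebound.

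**The plan's own figure.** The difference is 50.9 − 32.2 = 18.7, and its standard error is 33 × √(2/50) = 6.6, so the ratio is 2.83. Power is Φ(2.83 − 1.96) ≈ 80.9% by normal approximation and 80.1% by noncentral t. The stated 80% reproduces, and the sample size is not in dispute.

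**Threshold at Week 16 alone.** PASI at 125% of Baseline is a change of +25%. Assuming normality, P = 1 − Φ((25 − mean)/SD).

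| SD | Placebo | Active | Gap (points) |
|---|---|---|---|
| 25 | 1.1% | 0.1% | 1.0 |
| 33 (plan) | 1 − Φ(57.2/33) = 4.2% | 1 − Φ(75.9/33) = 1.1% | 3.1 |
| 40 | 7.6% | 2.9% | 4.7 |

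At SD 33 this is about 2.1 against 0.5 patients per 50, before the off-drug period begins.

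**What the tilt does to a real rebound.** Suppose a proportion r of active patients not already counted rebound after stopping, and no placebo patients do. The active rate becomes 0.0107 + 0.9893r, against 0.0415.

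- Break-even: r = 0.0308/0.9893 = 3.1%. Below this, the drug looks no worse than placebo.
- r = 5%: 6.0% against 4.2%, so +1.9 points (unrounded rates). Harm is still visible, but shrunk.
- r = 10%: 11.0% against 4.2%, so +6.8 points. Power at 50 per arm is about 25% by normal approximation (12% by Fisher's exact test). For a post-stop count with no placebo events it would be 63% (38%).

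**Counting any of Weeks 4 to 16.** This needs inputs the documents do not give. The assumptions here are Week 4, 8, 12 and 16 means at either 40/70/90/100% of the Week 16 mean or all equal to it, a common between-visit correlation of 0.5 to 0.9, and SD 25 or 33. Simulation then gives 2.2% to 20.7% on placebo and 0.3% to 11.7% on active, with a gap of about 2 to 9 points. Break-even r runs from about 2% (0.0196/0.9973) to about 10% (0.0902/0.8832).

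**Limits of the model.** Normality puts Φ((−100 + 50.9)/33) = 6.8% of active patients below −100%, which is impossible. The clinical part of the composite (new pustular, erythrodermic or more inflammatory disease) is not modelled. The direction of the gap is firm if the drug works; its size is not.

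**The case against.** **The word rebound already implies off-treatment.** That may be the intent, but no derivation rule says so, and the cumulative wording points the other way.

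**Off-drug information is reported elsewhere.** This stands. Week 20 PASI percentage change is compared with placebo by ANCOVA (Table 14.2.1.1.2), PASI change including Week 20 is analysed by MMRM (Table 14.2.2.6.1), PASI is listed by patient, and AEs and SAEs starting in the Follow-up period have their own tables (14.3.1.18 and 14.3.1.19). A reader might infer that the plan hides any withdrawal rebound or makes the Follow-up visit uninformative. The documents do not support that. What is missing is a post-stop rate for the defined event.

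**A reader might also infer that a true 5% rebound confined to active would be reported as a benefit.** The plan's own figures do not show this: with the Week 16 gap alone it appears as about 2 points of harm. Reversal requires assumed Week 4 to 12 profiles, and under the range above it may or may not occur.

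**Counting natural fluctuation on placebo is what a control is for.** Agreed. Relapse after washout can occur in every randomized arm, and no section quantifies it. The defect is the pooling of two periods, not the presence of a control.

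**It is one of several other secondary endpoints, with nominal p-values (SAP 7.1).** Also agreed. No section ties dose selection to rebound specifically.

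**Conclusion.** The point holds in this form: the endpoint cannot isolate rebound after stopping, and its planned active-minus-placebo comparison is tilted towards an effective drug. The pooling follows from the wording of both documents and needs no assumption. The direction of the tilt needs only that the drug reduces on-treatment worsening. The one size tied to the plan's figures is 4.2% against 1.1% at Week 16, a gap of about 3 points (1.0 to 4.7 for SD 25 to 40), and it rests on normality. The cumulative figures are illustrations. This is a defect of interpretation in a secondary endpoint that should be corrected before unblinding; it does not touch the primary analysis.

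**What to change.** Amend SAP 5.2 and 9.2.2 and the titles of Tables 14.2.2.11.1 and 14.2.2.11.2 as follows.

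1. Count as rebound only events first observed at the post-treatment assessment. For completers this is Week 20. For early discontinuers it is any observed assessment that dose dates show to be off drug, including the visit labelled Follow-up. Visit labels alone will not do, because SAP 7.4 can place an off-drug EOT visit in an on-treatment slot.
2. State that completers' Week 16/EOT visit is on-treatment. Protocol Table 4 dispenses no drug at Week 16, so for most completers that PASI falls hours after the last home dose. A bare after-the-last-dose rule would bring those Week 16 events back in.
3. Do not count patients who already met the criterion at their last on-treatment assessment.
4. Report on-treatment worsening to 125% of Baseline or more as a separate line.
5. Show change in PASI from the end-of-treatment value to Follow-up descriptively by arm. Step 1 keeps the Baseline anchor, and active patients enter Follow-up from a lower PASI, so some tilt remains.

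The cost is SAP wording and a derivation from visit and dose dates already collected. The downside is fewer events and a less precise rate: even with no events in 50 patients, the exact 95% upper limit is 1 − 0.025^(1/50) = 7.1%.

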6.2.2.3. Safety Endpoints

- The occurrence, severity, and seriousness of treatment-emergent adverse events (TEAEs) reported over the 16-week Treatment Period and the 4-week Follow-up Period.
- Changes from Baseline in physical examination; vital sign measurements (body temperature, respiration rate, heart rate, and systolic and diastolic blood pressure measurements); and body weight over the 16-week Treatment Period and the 4-week Follow-up Period.
- Changes from Baseline in ECG findings over the 16-week Treatment Period and the 4-week Follow-up Period.
- Changes from Baseline in safety laboratory values (hematology, serum chemistry, and urinalysis) over the 16-week Treatment Period and the 4-week Follow-up Period.
- HADS at each visit except Screening, Week 1 and Week 2.
- C-SSRS at each visit except Weeks 1 and 2.

6.2.3. Exploratory Endpoints

- Change from Baseline in Physician's Global Assessment of Fingernails (PGA-F) at Week 16.
- Change in scalp-specific Investigator Global Assessment (ss-IGA) from Baseline at Week 16 in the subgroup of patients with Baseline score of at least 2 (mild scalp psoriasis).

- Change from Baseline of scalp itch Numeric Rating Scale (NRS) at Week 16 in the subgroup of patients with Baseline score of at least 4 on the 11-point NRS.
- Change in cardiovascular risk factors at Week 16. The following parameters will be collected: weight, body mass index (BMI), waist and hip circumferences, blood pressure, fasting serum glucose, triglycerides, cholesterol (total and high-density lipoprotein / low-density lipoprotein fractions), and C-reactive protein.
- •
- Plasma levels of the drug and its metabolites at scheduled visits.

[figure not shown]
7. INVESTIGATIONAL PLAN

7.1. Description of Overall Study Design and Plan

This multicenter, randomized, double-blind, placebo-controlled, parallel-group, Phase 2b doseranging study is designed to assess the efficacy and safety of modified-release orismilast compared with placebo in adult patients with moderate-to-severe plaque-type psoriasis. Efficacy and safety outcomes will be evaluated to select an appropriate orismilast dose for subsequent Phase 3 studies. The study will be conducted in approximately 40 centers in Europe and North America.

After a Screening visit up to 28 days before Baseline, approximately 200 patients will be assigned randomly in a 1:1:1:1 ratio to receive 1 of the 3 orismilast doses (20 mg, 30 mg, or 40 mg) or placebo twice daily (BID) for 16 weeks, with a 4-week Follow-up visit. Administration will begin at Baseline with a dose titration period. The maximum duration of study participation is approximately 24 weeks.

Patients will be seen at the site on Screening, Baseline (Day 1), and Weeks 1, 2, 4, 8, 12, 16 (End-of-Treatment [EOT] visit), and 20 (Follow-up visit, 4 weeks after treatment completion or discontinuation). Visits at Weeks 1 and 2 could be conducted via a telemedicine procedure at Investigator's discretion.

N=50 Orismilast 20 mg BID (2 x 10 mg tablets) N=50 Orismilast 30 mg BID Screening (1 x 30 mg tablet and 1 x placebo tablet*) N=50 Orismilast 40 mg BID (1 x 10 mg tablet and 1 x 30 mg tablet) N=50 Placebo BID (2 x placebo tablets)* **Treatment Period** Follow up Randomization End of Period (16 weeks) Treatment (1:1:1:1)

Figure 1. Study Design

Abbreviation: BID, twice a day

7.2. Discussion of Study Design

A double-blind, randomized, placebo-controlled study is considered a gold-standard for conducting any interventional and dose-finding study. A sample size of 50 patients per treatment arm is also adequate to get robust outcome data for a comparison among doses and with placebo.

Psoriasis is a chronic condition requiring long-term therapy. Primary efficacy assessments of psoriasis clinical trials are usually performed at 12 or 16 weeks after initiation of study treatment. Because of the initial titration period of up to 2 weeks duration, a treatment duration of 16 weeks, with the primary endpoint being evaluated at this time point is, therefore, considered the optimal strategy for this study. Primary evaluations of apremilast, the only PDE4 inhibitor currently approved for psoriasis treatment, were also conducted at Week 16. A 16-week Treatment Period was also deemed acceptable for the placebo arm because psoriasis is not a life-threatening disease warranting immediate treatment.

Besides the usual psoriasis assessments including the PASI, the IGA, and the BSA, the effects of study treatment on nail and scalp psoriasis that represent location of disease more refractory to treatment will be explored. In patients with PsA, any potential effect on will be also assessed. A number of patient-reported outcome (PROs) will be administered to explore the patient's perception of his or her condition and the related QoL, as recommended by regulatory agencies. This comprehensive evaluation of the psoriatic condition of patients will contribute to the selection of the most suitable dose(s) for the Phase 3 clinical program.

^{*}To maintain the study blind.

7.3. End of Study

A patient will have fulfilled the requirements for study completion if/when the patient has completed all study periods, including the Follow-up visit or the last scheduled visit as indicated in the Schedule of Assessments (Table 4).

The end of the study will be the last patient's last visit as indicated in the Schedule of Assessments (Table 4).

8. SELECTION OF STUDY POPULATION

8.1. Inclusion Criteria

Patients are eligible to be included in the study only if all of the following criteria apply:

- 1. Capable of giving signed informed consent, which includes compliance with the requirements and restrictions listed in the Informed Consent Form (ICF) and in the protocol.
- 2. Male and female patients ≥ 18 years of age at the time of signing the ICF.
- 3. Body weight of >40 kg at the time of signing the ICF.
- 4. Diagnosis of chronic, stable plaque-type psoriasis at least 2 months before the Screening visit. If the patient is diagnosed with psoriasis arthritis, the arthritis should be stable.
- 5. Moderate-to-severe plaque-type psoriasis as defined by PASI \geq 12, BSA \geq 10%, and IGA \geq 3 at the screening and baseline visits.
- 6. Candidate for systemic antipsoriatic treatment or phototherapy.
- 7. Women of childbearing potential (WOCBP) must have a negative serum pregnancy test at the Screening visit and a negative urine pregnancy test at the Baseline visit. In addition, sexually active WOCBP must agree to use a highly effective method of contraception until at least 4 weeks after the end of study treatment. Highly effective methods of contraception are those that have a failure rate of <1% (when implemented consistently and correctly) and include hormonal contraceptives (combined oral contraceptive, patch, vaginal ring, injectable, or implantable); progestogen-only hormonal contraception associated with inhibition of ovulation (administration may be oral, injectable, or implantable); intrauterine devices or systems; self or partner vasectomy; or bilateral tubal ligation. Patients must have been on a stable dose of hormonal contraceptives for at least 4 weeks before the Baseline visit. Abstinence from heterosexual intercourse is an accepted method of contraception if it is the patient's lifestyle and is practiced for the entire duration of the study. Note: A woman of nonchildbearing potential is defined as a woman with surgical sterilization (hysterectomy, bilateral oophorectomy, or bilateral salpingectomy) or a woman in a postmenopausal status defined as cessation of menses for at least 12 months without an alternative medical cause and a confirmatory follicle-stimulating hormone (FSH) test or as cessation of menses for at least 24 months without an alternative medical cause.

